#### 4.1.3 Conduct of Statistical Analysis

██████████ will conduct the analysis. ██████████ will advise and discuss the approaches and provide domain knowledge.

R software will be used to analyse the data (versions of base and extension packages will be noted).

#### 4.1.4 Quality control on statistical analysis

██████████ will conduct quality control on the R code used, and the summarised data.

#### 4.1.5 Presentation of data

The report will conform to a conventional format with data completeness and population summaries (such as demographics).

Summary statistics will be provided for baseline characteristics for those patients reaching the 0.1 HUI3 gain at visit 1, and those who did not. Similarly, for those with baseline HUI hearing attribute categories  $\leq 3$  and those  $>3$ .

Univariate logistic models will be produced with estimated odds ratios and p-values will be presented. If feasible, multivariate logistic models will be produced. In addition, the predictive

capability of the model can be tested, and/or the threshold criterion varied (e.g. via RoC) to obtain higher predictive power.

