## 4 FACTORS INFLUENCING QOL OUTCOMES WITH CI

To differentiate from previous publication the approach will be to establish odds of improvement in HUI Mk III scores. The minimum clinically important change/difference in HUI3 is 0.03 units, but an alternative higher cut-off may be used (or in addition, see below). The aim is to give recommendations on the characteristic/s which are most likely to provide significant health utility from a CI.

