## 4.1 Statistics

### 4.1.1 Sample Size

The decision of success/fail in significant impact of CI on HUI3 scores requires paired pre/post data in order to test the difference scores. Currently one centre has good follow-up, ZA-01, and overall a high number of patients with 161 at baseline and 117 at 1 year as of December 2019. Thus approximately 110 datapoints are available.

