#### 4.1.2.1 Pass/Fail Criteria

[figure not shown]
The minimum clinically important change/difference in HUI3 is 0.03 units. For HUI3 this change is very small and larger mean differences are typically observed. As such for these analyses we are interested in differences/changes of at least 0.1 units. Below is summarised the simple paired comparison of baseline versus 1-year HUI3 scores:

```
> t.test(dat.w.temp$hui.v3.score.multi.1,dat.w.temp$hui.v3.score.multi.0, p
aired=TRUE)
```

```
Paired t-test
```

```
data: dat.w.temp$hui.v3.score.multi.1 and dat.w.temp$hui.v3.score.multi.0
t = 5.9659, df = 132, p-value = 2.105e-08
alternative hypothesis: true difference in means is not equal to 0
95 percent confidence interval:
 0.09963182 0.19847490
sample estimates:
mean of the differences
      0.1490534
```

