### Histogram of dat.w.temp\$hui.v3.score.multi.1 - dat.w.temp\$hui.v3.score.mul

The mean difference score is 0.149, with a confidence interval of ~0.1 to ~0.2. As stated above, 0.1 is generally considered to indicate a highly significant individual gain in HRQoL. Based on the histogram above, somewhat more than 50% of cases achieved a HUI3 gain of >0.1. An approximate cut-off representing 50% of cases is a good basis for a success/fail criterion for a logistic analysis (i.e. median gain in HUI3 for example). However, it may be useful to tune the criterion to improve the predictive performance of the model once initial results are obtained for gain = 0.1.

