#### 4.1.2.2 Primary Hypothesis and Analysis

Once the criterion for “significant gain” in HUI3 is defined, the baseline characteristics of those meeting and not meeting the criterion can be compared. Then it can be hypothesised that those characteristics which are divergent for the group may influence significant gain in HUI3 scores.

Typical factors to consider are etiology, age, duration of hearing loss/deafness, onset of hearing loss, use of hearing aids, tinnitus status, and dizziness status. There are too many etiology categories compared to the total N of subjects so they will be grouped as in Table 1.

For the effects of age, continuous variable or range groups may be evaluated (i.e. approximate ABS age as in Section 1 above will be used unless sample sizes are too small).

Onset of deafness in childhood, or “congenital” deafness may be calculated from age and duration of hearing loss. In consultation with the centre, “pre-linguistic” onset of deafness is

[figure not shown]
defined as <10 years of age. Arguably “congenital” deafness should be limited to ages <2 (for the purposes of identification). The other defined onsets are progressive and sudden HL.

Table 1. Etiologies (implanted ear) at baseline grouped for ZA-01.

Familial	7
Vestibular ( Large vestibular aqueduct Menieres syndrome)	8
Meningitis	8
Viral, (measles and mumps rubella)	9
Ototoxic drugs	11
Middle ear: Cholesteatoma, Congenital atresia, Otosclerosis	15
Other	27
Unknown	75

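### SAP Section 4 lets the logistic model's predictive performance be tested and its success criterion tuned, but names no validation data or method; if measured on the fitting data, performance is biased upward

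*SAP*

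**What the plan says.** SAP Section 4 states its purpose: "The aim is to give recommendations on the characteristic/s which are most likely to provide significant health utility" from an implant. The data are described in SAP 4.1.1: one centre, ZA-01, with "161 at baseline and 117 at 1 year as of December 2019", leading to "Thus approximately 110 datapoints are available".

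SAP 4.1.2.1 starts from a gain of 0.1 as the success criterion. The text under its histogram then allows that criterion to be adjusted after the first results are seen, so that the model predicts better.

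SAP 4.1.2.2 gives the candidate predictors: "Typical factors to consider are etiology, age, duration of hearing loss/deafness, onset of hearing loss, use of hearing aids, tinnitus status, and dizziness status". On etiology it says "There are too many etiology categories compared to the total N of subjects so they will be grouped as in Table 1"; that table has eight groups. SAP 4.1.2.3 adds the baseline HUI3 hearing attribute, split in two.

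SAP 4.1.5 commits to univariate logistic models with odds ratios and p-values, and to multivariable models if feasible. It then says that the predictive "capability of the model can be tested", and/or the threshold varied, for example by ROC, to raise predictive power. The threshold could be the HUI3 gain cut-off or a probability cut-point; the text does not say which.

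Neither document mentions a hold-out sample, a second centre for validation, cross-validation, bootstrap or shrinkage for this model. Quality control in SAP 4.1.4 covers the R code and the summarised data.

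**The concern.** A logistic model ranks the patients it was fitted to better than it ranks new ones, because the coefficients have absorbed the chance pattern in that sample. This optimism grows with the number of coefficients per patient in the smaller outcome class. It grows again when the outcome definition or the classification threshold is chosen for the best result. Section 4 combines a small sample, a long factor list and permission to tune, with nothing to separate real discrimination from optimism.

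The bias does not depend on how the factors or the cut-off are chosen. With both fixed in advance, performance measured on the fitting data would still be too high. At stake is any published statement that these baseline characteristics predict who gains: an AUC around 0.70 would normally be read as moderate discrimination. The SAP introduction also waives reporting of deviations from the plan, so a reader could not tell which validation, if any, had been intended.

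**Working it through.** **1. The SAP's own figures.** The 110 is a count, not the result of a formula. It is consistent with the 117 patients seen at 1 year, being below it. The t-test in SAP 4.1.2.1 can be rebuilt from "t = 5.9659, df = 132, p-value = 2.105e-08" and the mean difference of 0.14905:
- SE = 0.14905 / 5.9659 = 0.02498.
- 95% CI = 0.14905 ± 1.978 × 0.02498 = 0.0996 to 0.1985, matching the SAP; p = 2.10e-08, also matching.
- Pairs = 132 + 1 = 133. SD of gain = 0.02498 × √133 = 0.288.

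The hearing-attribute table in SAP 4.1.2.3 also sums to 133. That exceeds ZA-01's 117 at 1 year, so it is either a wider set of patients or a different data cut. Both 110 and 133 were therefore used below.

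**2. Share of successes.** The SAP says "somewhat more than 50% of cases achieved a HUI3 gain of >0.1". A normal distribution with mean 0.149 and SD 0.288 gives P(gain > 0.1) = Φ(0.049 / 0.288) = 0.568, so the smaller class is about 43%.

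**3. Number of coefficients.**
- Smaller full model: etiology 7, age 1 (continuous), duration 1, onset 2 (three levels assumed), hearing-aid use 1, tinnitus 1, dizziness 1. Total 14.
- Larger full model: age in five groups (4 instead of 1) plus the baseline hearing attribute (1). Total 14 + 3 + 1 = 18.
- Patients in the smaller class per coefficient at n=110: 110 × 0.433 / 14 = 3.4, and 110 × 0.433 / 18 = 2.6.

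**4. Simulation under no effect.** The outcome was generated independently of every predictor. Etiology followed the frequencies in Table 1 of SAP 4.1.2.2 (total 160). Assumptions not in the documents: predictors independent of each other; hearing-aid use, tinnitus and dizziness at 50% prevalence. The fit was maximum likelihood with a negligible ridge term, 600 replicates per setting. AUC = [R₁ − n₁(n₁+1)/2] / (n₁n₀), where R₁ is the rank sum of the fitted scores among successes. True AUC was measured in 4,000 new patients.

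| n | Coefficients | Mean apparent AUC (5th–95th percentile) | Runs with AUC ≥ 0.70 | AUC in new patients |
|---|---|---|---|---|
| 110 | 14 | 0.70 (0.64–0.77) | 50% | 0.50 |
| 110 | 18 | 0.73 (0.67–0.80) | 80% | 0.50 |
| 133 | 14 | 0.68 (0.62–0.74) | 30% | 0.50 |
| 133 | 18 | 0.71 (0.65–0.77) | 64% | 0.50 |

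At n=110, the best ROC cut-point gives apparent sensitivity and specificity of about 0.68 and 0.68 (14 coefficients), or 0.70 and 0.71 (18).

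**5. Tuning the outcome cut-off.** Taking the best of 0.03, 0.05, 0.1, 0.15 and 0.2 (an assumed set; 0.03 and 0.1 are the SAP's) raises the mean apparent AUC at n=110 to 0.73 (14 coefficients) and 0.76 (18). It reaches 0.70 in 81% and 97% of runs.

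**6. Smaller models, n=110.**
- Full list without etiology (14 − 7 = 7 coefficients): about 0.64, reaching 0.70 in about 4% of runs.
- Five coefficients (age, duration and the three binary factors): 0.62, reaching 0.70 in under 1% of runs.
- Single factors: about 0.54 to 0.55, except etiology alone at 0.62.

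**7. What validation recovers, pure noise, n=110.**
- Repeated 5-fold cross-validation (14 coefficients, 400 replicates): mean 0.50, 5th–95th percentile 0.38 to 0.61.
- Bootstrap optimism correction: about 0.57 (14 coefficients) and 0.58 (18). These are rougher figures, from 60 datasets with 60 resamples each. The correction removes most of the optimism but not all.

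**The case against.** The strongest reply is that the SAP commits to very little here. Predictive testing is optional and multivariable models depend on feasibility. The firm outputs are summaries, univariate odds ratios and p-values. An AUC is never named as an output; ROC appears once in Section 4, attached to varying the threshold. No dataset is named for the test, so resampling or other patients are not excluded: SAP 4.1.1 says only that one centre currently has good follow-up, and SAP 2.3.1 counts 1361 baseline records across all device types. The 0.70 also needs a near-maximal model at 3.4 smaller-class patients per coefficient. The SAP already groups etiologies because of limited numbers, so that model may never be fitted. Finally, recommendations on characteristics can rest on odds ratios, and Section 4 does not mention counselling; that word belongs to the age analysis in SAP 1.3.2.2.

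Most of this stands, and it limits the point to a conditional one. It does not remove it. An analysis that the plan offers, with higher predictive power as its stated goal, needs a stated way of being done validly. The one-centre set is the only sample that Section 4 gives for this model. The same optimism affects sensitivity and specificity, so the absence of the term AUC does not help. The permission to tune the criterion on results is explicit and works in the same direction.

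**Conclusion.** The gap is real: predictive testing and criterion tuning are permitted, and no validation data or method is stated. If performance is measured on the fitting data, the full model on the SAP's own factor list shows an apparent AUC of about 0.70 from pure noise at n=110 (0.68 at n=133), and cut-off tuning adds about 0.03. This rests on assumed independent predictors, assumed prevalences and three onset levels. The bias is moderate without etiology and slight for most univariate models.

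A reader might infer that the SAP plans uncorrected testing in the same 110 patients, and that any noise model would therefore look useful. The documents do not support that. Same-sample testing is inferred from silence, and the large bias belongs to the optional full model. Nor do the documents make the recommendations depend on an AUC.

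**What to change.** Add to SAP 4.1.5:
- Any AUC, ROC or classification result will be internally validated by repeated k-fold cross-validation. Bootstrap optimism correction is acceptable if its residual optimism at this sample size is noted.
- Every factor-selection and cut-off-tuning step will be repeated inside the resampling.
- The validated value will be shown beside the apparent value, and any statement about predictive ability will rest on the validated value only.

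An interval should accompany the validated value: cross-validation is centred correctly under noise, but the single-study spread of 0.38 to 0.61 is wide. SAP 4.1.1 should also say whether the model uses the roughly 110 ZA-01 pairs or the 133 in the t-test.

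The cost is a few sentences and a few lines of R, with no new data. The downside is a less favourable reported figure.

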## 5 HEARING PRESERVATION PER DEVICE TYPE

Not currently applicable.

## 7 CHANGE HISTORY

Version	Change	Author	Date
1	Original version		5 Nov 2019

## 8 DEFINITIONS

Term	Description
LMM	Linear mixed model, for repeated measure analyses
GLM	General linear model, for example employing a non-linear link function
GLMM	General linear mixed model, for repeated measure analyses
HUI	Health Utilities Index (in this case mark III, or HUI3 for short)
SSQ	Speech, spatial and qualities (score from questionnaire)
